6.5.1 Figures for primary and key secondary endpoints

A plot with the results from the statistical analyses in the testing hierarchy will be presented. In addition, plots with 2 y-axes will be presented (the daily pollen count and average TCS, DSS and DMS) relative to day from TPS start for each cohort.

6.6 Additional endpoints analyses

6.7 Secondary endpoints

The following secondary endpoints will be analysed identically to the primary endpoint using the main estimator for the trial product estimand:

- Average TCS during the AHPS and OPS
- Average DSS during the AHPS and OPS
- Average DMS during the AHPS and OPS
- Average TCS (EAACI scoring) during BPS and TPS

Following endpoints will be analysed under the hypothetical strategy using the same intercurrent events and imputation approach defined for the main estimator.

- Proportion of severe days during BPS and TPS
- Proportion of well days during BPS and TPS
- Proportion of symptom-free days during BPS and TPS

The proportion of severe days during BPS will be analysed using a GLMM with a logit link function. For the proportion of severe days during BPS the model will include “number of severe days/total number of days in BPS” as the response variable and treatment, cohort and age group as fixed effects and pollen station within cohort as random effects. From the GLMM model, the odds ratio of having a severe day of active treatment relative to placebo will be presented together with the corresponding p-values and 95% confidence limits. The endpoints proportion of severe days during TPS, proportion of well days during BPS and TPS, and symptom-free days during BPS and TPS will be analysed using the same model as for severe days during BPS. The imputation of missing data of aforementioned endpoints, will be done by using unrestricted random sampling method, which utilises selection with equal probability and with replacement. For each subject with missing data, the number of days in pollen season as well as the number of days with the endpoint of interest will be replaced from the pool of completed subjects with non-missing data in the same age group and the treatment group according to hypothetical strategy.

A plot with the results from the statistical analyses of the endpoints proportion of severe days, proportion of well days and proportion of symptom-free days during BPS will be presented. The plot will include estimated proportions of having a severe day, well day and symptom free days, the relative difference including 95% CI, and a p-values.

The endpoint percentage of patients free of symptoms and with no use of rescue medication during the BPS and TPS will be summarised. The endpoint will be categorised as a binary variable (0/1). A subject will be considered as responder if he/she has no symptoms and has not used rescue medication during an entire season (BPS or TPS).

6.7.1 Questionnaires

The endpoint average weekly overall RQLQ(S) score during the BPS and TPS respectively will be analysed using the same model as for the main estimator and sensitivity estimator for the trial product estimand and supportive analysis, except for not square rooting the endpoint and including age group as a fixed effect, i.e., the model will include treatment, and cohort as fixed effects and pollen station within cohort as a random effect, with different residual errors specified for each treatment group. The overall PRQLQ will be analysed using the same approach and model as for RQLQ.

In addition to above the average weekly overall RQLQ(S) score during the BPS and TPS will be summarised.

The endpoint patient-rated global evaluation of treatment efficacy at EOT categorised as a binary variable (improvement versus no improvement) will be analysed by using a GLIMM with a logit link function, under the hypothetical strategy using the same intercurrent event and imputation approach defined for the main estimator. The assessment is made at EOT and each subjects had to respond to the question using the 5-point scale: much better, better, the same, worse, much worse. A subject is considered as responder if she/he feels better or much better (improvement=1), otherwise it's considered as a non-responder (improvement=0). The model includes the binary endpoint (improvement/no improvement) as response variable and treatment, cohort and age group as fixed effects and pollen station within cohort as random effects. From the GLMM model, the odds ratio of having an improvement at EOT of active treatment relative to placebo will be presented together with the corresponding p-values and 95% CI.

TSQM-9 using the convenience domain for subjects 5 to less than 12 years at EOT will be analysed similar to average weekly overall RQLQ(S) score and overall PRQLQ using the main estimator for trial product estimand.

Summary of TSQM-9 by domains (effectiveness, convenience, global satisfaction) and treatment will be presented.

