2.10 Secondary efficacy endpoints

Additional secondary efficacy endpoints are:

- Average TCS, average DSS and average DMS during the alder-hazel (AHPS) and oak • pollen seasons (OPS)
- Number of severe days during the BPS and TPS, where a severe day is defined by a DSS • ≥6 and where ≥2 symptoms are assessed as moderate or 1 symptom is assessed as severe
- Number of well days during the BPS and TPS, where a well day is defined as no use of • rescue medication and DSS ≤2
- Number of symptom-free days during the BPS and TPS, where a symptom-free day is • defined as one with no symptoms and with no use of rescue medication
- Percentage of patients free of symptoms and with no use of rescue medication during the • **BPS and TPS**
- Average TCS (EAACI scoring) during the BPS and TPS •
- Average weekly overall RQLQ score during the BPS and TPS (12-17 years only) •
- Overall PRQLQ score during the BPS (5-11 years only)
- Treatment satisfaction (TSQM-9) evaluations
- Patient-rated global evaluation of treatment efficacy

Immunology endpoints:

- Change from baseline in birch specific IgE and IgG₄
- Change from baseline in alder, hazel and oak specific IgE and IgG₄ (for a subgroup of • randomised subjects only)
- Change from baseline in birch, alder and hazel specific IgE-BF (for a subgroup of • randomised subjects only)

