15.9.11 Treatment satisfaction (TSQM) evaluation scores

The TSQM-9 consists of 9 items covering 3 domains (Effectiveness, Convenience, Global satisfaction). Items are scored on either a 5-point (1-5) scale or 7-point (1-7) scale, where higher scores indicate greater treatment satisfaction. For each domain, item scores are summed and normalised to a 0-100 scale, where 0 is the worst possible level of satisfaction and 100 is the best possible level of satisfaction.

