15.12.6 Secondary efficacy analyses

The following secondary endpoints will be analysed identically to the primary endpoint using the estimators of the trial product and treatment policy estimands: average TCS, average DSS and average DMS during the AHPS and OPS, average TCS (EAACI scoring)

Proportion of severe days, proportion of well days, proportion of symptom-free days and patientrated global evaluation of treatment efficacy (categorised as improvement versus no improvement) will be analysed with a logistic regression model with treatment, pollen season and age group as fixed effects and pollen station (or region) as random effects.

Average weekly overall RQLQ scores during the BPS and TPS, overall PRQLQ scores during the BPS and TSQM-9 domain scores will be analysed with a linear mixed model.

Change from baseline in immunological endpoints will be analysed with a repeated measures linear mixed model.

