Changes to the analyses and changes that might impact the analyses described in the CTP are documented in section 6.11.

Supporting documentation is provided in section 9. Section 9.1 'Definition of pollen seasons' contains the definition of start and end dates for the different pollen seasons used in the trial. Section 9.2 'Derivations for the trial' contains details about the derivations used in the trial.

In addition to above, the SAP includes several appendices (section 11). Appendix A includes a list of terms used to identify local administration site TEAEs, further details about the statistical analyses are provided in Appendix B, examples of SAS code are listed in Appendix C, and Appendix D includes the start and end dates of the pollen station.

This SAP has been written and approved before database lock and unblinding.

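### SAP 6.7.1 models only TSQM-9 convenience in children under 12, where the protocol plans a mixed model of the domain scores without restriction, and 6.11 does not declare the narrowing

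*SAP*

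**What the plan says.** **Protocol.** Section 2.10 lists "Treatment satisfaction (TSQM-9) evaluations" among the secondary efficacy endpoints. The RQLQ and PRQLQ entries just above it carry age limits; this one does not. Section 15.9.11 describes the instrument: "The TSQM-9 consists of 9 items covering 3 domains (Effectiveness, Convenience, Global satisfaction"). Section 15.12.6 gives the analysis: "TSQM-9 domain scores will be analysed with a linear mixed model". The next sentence there covers the antibodies: "Change from baseline in immunological endpoints will be analysed with a repeated measures linear mixed model".

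**SAP.** Section 6.7.1 contains two sentences on TSQM-9. The first reads "TSQM-9 using the convenience domain for subjects 5 to less than 12 years at EOT will be analysed", and goes on to apply the RQLQ/PRQLQ approach under the main estimator of the trial product estimand. The second reads "Summary of TSQM-9 by domains (effectiveness, convenience, global satisfaction) and treatment will be presented". Section 6.7.2 fits the repeated measures model to birch IgE, birch IgG4 and birch IgE-BF. It summarises the alder, hazel and oak IgE and IgG4 and the alder and hazel IgE-BF.

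**Declaring changes.** SAP section 3 states: "Changes to the analyses and changes that might impact the analyses described in the CTP are documented in section 6.11". Section 6.11 mentions neither TSQM-9 nor the modelling of the secondary immunology endpoints.

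**The concern.** The protocol plans a modelled comparison of the TSQM-9 domain scores. The SAP keeps it for one domain in one age band and gives no reason for that choice in the public text. Effectiveness and global satisfaction, the two domains closest to efficacy, are left without an adjusted difference or confidence interval.

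The silence in 6.11 matters because that section is otherwise detailed. It records percentiles dropped from tables and a band plot replacing a Kaplan-Meier plot. It also records a comparable narrowing, in which the alder-hazel and oak season scores and the EAACI score are limited to one estimand and one estimator. A reader would take an analysis not listed there to be unchanged. Protocol section 15 asks the trial report to document changes relative to the final SAP, so a protocol-to-SAP change that 6.11 omits need not come to light later.

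**Working it through.** The documents give no sample size or power for TSQM-9, so there is no stated figure to reproduce. The check is a comparison of texts and a count.

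**Inputs**
- Domains: 3 (protocol 15.9.11; SAP 9.2.4.3).
- Age groups: 2, 5-11 and 12-17 years. About 45% of about 1000 randomised subjects are to be aged 5-11 (protocol 3.1).
- Data collection: the protocol flow chart has TSQM-9 completed by subjects of all ages, at visit 6 or, for some cohort 1 subjects, by telephone after the tree pollen season.
- Multiplicity: TSQM-9 is not among the nine hypotheses of the hierarchy (protocol 15.11; SAP 4.1.1).

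**TSQM-9 under the SAP** (the protocol sets no limit, so every cell would be modelled)

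| Domain | 5-11 years | 12-17 years |
|---|---|---|
| Convenience | modelled | summary only |
| Effectiveness | summary only | summary only |
| Global satisfaction | summary only | summary only |

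Protocol: 3 × 2 = 6 cells modelled. SAP: 1 of 6.

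**Subjects**
- 5-11 years: 0.45 × 1000 = 450.
- 12-17 years: 0.55 × 1000 = 550.

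There are two separate losses. For effectiveness and global satisfaction, the model is lost for all of the roughly 1000 subjects. For convenience, it is lost for about 550 (55%).

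**Precision for convenience, for scale only.** Assume 1:1 allocation, 80% power, two-sided 5%, a simple two-group comparison and no missing data. The detectable standardised difference is (1.960 + 0.842) × √(2/n), with n per arm.
- All ages, n = 500: 2.802 × √(2/500) = 0.18 SD.
- 5-11 years only, n = 225: 2.802 × √(2/225) = 0.26 SD.

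**Immunology.** Protocol 2.10 lists birch IgE and IgG4 (2 parameters), alder, hazel and oak IgE and IgG4 (3 × 2 = 6), and birch, alder and hazel IgE-BF (3), which is 2 + 6 + 3 = 11. SAP 6.7.2 models 3, all birch, and only summarises 11 − 3 = 8. The antibody item in 6.11 concerns an exploratory assessment and does not cover these secondary endpoints.

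**The case against.** The strongest reply is that little is lost and one line in 6.11 would repair it. Several parts of this stand.

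- The other domains are not dropped. They are summarised by arm, and SAP 6.1 provides means and standard deviations by treatment group, from which an unadjusted difference can be derived.
- A reader might infer that the trial can no longer answer its satisfaction objective. The documents do not support that. SAP Table 1 pairs that objective with the patient-rated global evaluation and places TSQM-9 under quality of life (a shifted row in the extracted table is possible). Section 6.7.1 models the global evaluation at all ages and reports an odds ratio with confidence interval.
- A reader might also infer outcome-driven selection. Nothing in the text shows it: the SAP states that it was approved before database lock and unblinding, and it calls analyses outside the hierarchy supportive.
- The protocol says domain scores, not all domain scores, gives no model terms for TSQM-9, and leaves detail to the SAP. Even so, with no restriction stated and three domains defined, the plain reading is all three at all ages. Removing a planned comparison goes beyond adding detail.
- SAP section 6.8 is not visible in the public text. Further TSQM-9 modelling there cannot be excluded. It is unlikely, because TSQM-9 is a secondary endpoint handled in 6.7.1.

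A line in 6.11 would cure the lack of disclosure. It would not supply the adjusted estimates and intervals that the protocol planned.

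**Conclusion.** The point holds as an undeclared reduction of a protocol-planned secondary analysis. One of six domain-by-age combinations keeps a model-based between-arm estimate. Effectiveness and global satisfaction have none at any age, and convenience has none in the roughly 55% of subjects aged 12-17. Eight of eleven secondary antibody parameters lose their model in the same way.

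The consequence is moderate. The satisfaction objective is still partly addressed by the modelled global evaluation, and the type I error of the nine hierarchical tests is unaffected. The point concerns completeness and transparency; bias has not been shown.

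This rests on reading the unrestricted protocol sentence as covering all domains and ages, on the planned 45/55 age split, and on no further TSQM-9 model in the unseen section 6.8.

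**What to change.** **TSQM-9 (SAP 6.7.1).** Analyse all three domain scores in the FAS with the RQLQ-type mixed model: untransformed score, treatment and cohort as fixed effects, pollen station within cohort as a random effect, and separate residual variances by arm. Add age group as a fixed effect, since both age groups are now included. Report the results as supportive, outside the hierarchy. Keep convenience in subjects aged 5 to under 12 as a subgroup result. State whether the end-of-treatment wording there fixes the subject's age or the time of assessment, because the RQLQ and PRQLQ age bands are set at randomisation.

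**Immunology (SAP 6.7.2).** Either restore the repeated measures models for the alder, hazel and oak parameters in the SUB set, or list their omission in 6.11 with the reason.

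**Cost.** A few extra runs of models already specified, on data already collected, and more supportive p-values without multiplicity control.

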6.7.2 Immunology

The following immunology endpoints will be summarised by visit and treatment including change from baseline:

- Birch specific IgE, $\log_{10}(\text{IgE})$, $\log_{10}(\text{IgG}_4)$.
- Alder, hazel and oak specific $\log_{10}(\text{IgE})$ and $\log_{10}(\text{IgG}_4)$ (SUB)
- Birch, alder, and hazel specific IgE-BF (SUB)

Change from baseline in birch specific $\log_{10}(\text{IgE})$ and $\log_{10}(\text{IgG}_4)$ at visit 4 and 6 will be analysed using repeated measures linear mixed model. The model includes change from baseline of the log-transformed immunological parameter as response variable and the log-transformed immunological parameter at baseline, treatment, visit and treatment*visit interaction as fixed effects, and subject as random effect. The active group will be compared to placebo at each visit using a t-test in the linear mixed model. The corresponding difference in adjusted means (placebo vs active) will be calculated together with the associated p-value and 95% CI. In addition, the back-transformed adjusted mean and relative difference in back-transformed adjusted means including 95% CI will be listed. The analysis will be based on observed case and FAS.

The birch specific IgE-BF will be analysed using the same model as for IgE and IgG₄, without log transforming the endpoint and the fixed effect IgE-BF parameter at baseline. The analysis will be based on observed case and SUB.

Plots of change from baseline in birch specific $\log_{10}(\text{IgE})$, $\log_{10}(\text{IgG}_4)$, and IgE-BF in adjusted means will be displayed by treatment with 95% CI.

When taking the logarithm, values below the LLOQ of IgE and IgG₄ will be given the minimum value measured above 0 for IgE and IgG₄ and. Otherwise, data is used as measured.

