3.2.3 Randomisation

The randomisation list has been generated by the IRT provider and will not be accessible to trial personnel involved in the conduct of the trial, until the database has been locked. The randomisation was administered centrally via IRT and was stratified based on country and age group.

The randomisation codes will only be made available for data analysis when the clinical database has been locked and all PDs have been identified, evaluated, categorised, and closed.

4 Statistical hypotheses

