For the purposes of analysis, the analysis sets presented in

Table 4 are defined.

Table 4: Analysis set definitions

Participant analysis set	Description	Application
TAS	All subjects who signed informed consent and thus includes screening failures.	Outputs related to disposition.
FAS	All randomised subjects. Subjects will be analysed as randomised i.e., according to their randomised assignment of treatment.	Outputs related to baseline and efficacy outputs.
SAF	All randomised subjects who received at least one dose of IMP. Subjects will be analysed as treated i.e., according to treatment they actually received.	Outputs related to safety reporting.
SUB	Subjects in a random subset sample stratified by treatment group and age group for cohort 1.	Endpoints related to alder, hazel and oak specific IgE and IgG4, and birch, alder, and hazel specific IgE-BF.

[REDACTED]
[REDACTED]

The following DPS are defined:

DPS1: For subjects who complete the trial treatment, all data is included.

For subjects who discontinue trial treatment, all data collected after the time of trial treatment discontinuation will not be included for the trial product estimand.

DPS2: All data is included.

FAS and DPS1 are used to estimate the trial product estimand, FAS and DPS2 are used to estimate the treatment policy estimand and observed case.

6 Statistical analyses

Statistical analyses will be carried out by ALK, Biometrics, Hørsholm, Denmark. All computation will be performed using SAS, SAS® version 9.4 or later.

The analyses described in this section along with the supporting information supplied in section 9 and Appendix B specify the statistical analyses.

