6.3 Primary endpoint analysis

6.3.1 Definition of endpoint

The primary endpoint is the average TCS during the BPS. The average TCS during the BPS is the average of the daily sum of the DSS and DMS during the BPS.

6.3.2 Main estimator, sensitivity estimator(s) and statistical analysis for the trial product and treatment policy estimands

The main estimator for both estimands will be the absolute treatment difference.

The main estimator for both estimands will be based on an identical method of statistical analysis (specified below), although the actual data used in each analysis may vary according to the different strategies taken for the handling of intercurrent events and missing data. Further details of the different strategies for each estimand are provided in sections 6.3.3.1, 6.3.3.2, and 6.4.1.

Analyses will be based on all randomised subjects. Subjects for whom the efficacy endpoint is missing will be included in the analysis through multiple imputation, where missing data will be

imputed from the same age group according to the approaches specified in sections 6.3.3.1, 6.3.3.2, and 6.4.1. Imputation will use the method of unrestricted random sampling with replacement (seed=7127) and 1000 multiply imputed datasets will be created. For each dataset, the efficacy endpoint will be square root transformed in order for the residuals to fulfil the underlying assumption of following the so-called statistical normal distribution and analysed using a linear mixed effects model assuming unequal variances in the 2 treatment groups. The model will include treatment, cohort (1, 2), and age group (5-11 years, 12-17 years) as fixed effects and pollen station within cohort as a random effect, with different residual errors specified for each treatment group. The model will be estimated using REML, and the denominator degrees of freedom will be calculated using the Kenward and Roger's approximation (Kenward and Roger 1997).

Rubin's rule is used to combine the 1000 analysis results across the multiple imputed datasets. The p-value for the absolute difference is reported as the test result.

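### The immunology model gives visits 4 and 6 one shared variance and leaves out age group, cohort and pollen station, so its visit-specific confidence intervals may have the wrong width

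*SAP*

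**What the plan says.** SAP 6.7.2 takes change from baseline in log-transformed birch IgE and IgG4 "at visit 4 and 6 will be analysed using repeated measures linear mixed model". Besides the baseline value, the terms are "treatment, visit and treatment*visit interaction as fixed effects, and subject as random effect". For the comparison, "The active group will be compared to placebo at each visit using a t-test in the linear mixed model", with a p-value and 95% CI. Birch IgE-BF uses the same model without the log. The IgE and IgG4 models use observed cases in the FAS. IgE-BF uses SUB, which SAP section 5 (Table 4) defines as "Subjects in a random subset sample stratified by treatment group and age group for cohort 1". The alder, hazel and oak parameters are only summarised.

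Other sections bear on the point:

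- SAP 3.2.3: randomisation was "stratified based on country and age group".
- SAP 6.3.2: the primary efficacy model has "treatment, cohort (1, 2), and age group (5-11 years, 12-17 years) as fixed effects and pollen station within cohort as a random effect". Residual variance may differ between the two arms.
- Protocol 15.12.6 asks only for a repeated measures linear mixed model for immunology and fixes neither covariates nor covariance. The SAP therefore does not depart from it.
- SAP Appendix C gives code for the primary and the proportion analyses, none for immunology.
- SAP 4.1.1 places the immunology endpoints outside the testing hierarchy.

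**The concern.** There are two separate issues.

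**Variance by visit.** A random subject effect with a single residual is compound symmetry: one variance, shared by the visit before the season and the visit after it. An interval reported for one visit should rest on the variance at that visit. If the spread differs, pooling overstates precision at one visit and understates it at the other.

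**Covariates.** Age group was a randomisation stratum and was also used to draw SUB, but it is not in the model. Cohort and pollen station, which the FAS efficacy models carry, are also missing from the FAS immunology models. SAP 6.7.1 drops age group for RQLQ and PRQLQ, where each questionnaire is confined to one age band; that does not apply here, and no other reason is given.

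At stake is how far the reported visit-specific CIs and p-values for the immunological response can be trusted. No primary or key secondary result depends on them.

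**Working it through.** **No plan figure to reproduce.** The documents give no SD, effect size or power for immunology. Their only power figures concern the primary endpoint. A normal approximation for the FAS case uses a difference of 2.5 − 2.5·√(1 − 0.2375) = 0.317, SD 1.4 and 500 per arm. It gives 94.7% against the stated 95.0%. The observed-case figure comes out at 94.8% against 94.7%. Both agree, but neither informs this point.

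**Step 1: one variance for two visits.** Let k be the SD at the more variable visit divided by the SD at the other. k is an assumption. With complete data the model uses the average variance, (1 + k²)/2, at both visits. Relative to the correct width:

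- less variable visit: √((1 + k²)/2)
- more variable visit: √((1 + k²)/2)/k
- coverage: 2Φ(1.96 × factor) − 1

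For k = 1.5, (1 + 2.25)/2 = 1.625 and √1.625 = 1.275. The factors are 1.275 and 1.275/1.5 = 0.850.

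| k | More variable visit: width factor | Coverage | Less variable visit: width factor | Coverage |
|---|---|---|---|---|
| 1.0 | 1.000 | 95.0% | 1.000 | 95.0% |
| 1.1 | 0.956 | 93.9% | 1.051 | 96.1% |
| 1.25 | 0.906 | 92.4% | 1.132 | 97.4% |
| 1.5 | 0.850 | 90.4% | 1.275 | 98.7% |

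Twenty REML fits of a random-intercept model with 500 per arm, the visit 6 SD set to 1.5 times that of visit 4 and an assumed within-subject correlation of 0.6 gave a mean SE of 0.080 at both visits. The true values were √(2/500) = 0.063 at visit 4 and 1.5 × 0.063 = 0.095 at visit 6.

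**Step 2: omitted covariates.** If factors balanced between the arms explain a share R² of the residual variance, leaving them out multiplies the width by 1/√(1 − R²). R² is also an assumption: 0% gives 1.000, 1% gives 1.005, 5% gives 1.026 and 10% gives 1.054. The intervals can become wider, not misleadingly narrow.

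**Step 3: which change repairs what.** In simulation (500 per arm, 2000 trials, visit 6 SD 1.5 times visit 4, R² = 5%, correlation 0.6), results at visit 6 were:

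| Model | Coverage | Half-width |
|---|---|---|
| SAP 6.7.2 as written | 90.3% | 0.158 |
| plus age group and cohort | 90.1% | 0.154 |
| plus age group, cohort and visit-specific variances | 95.2% | 0.182 |

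Only the visit-specific variance restores coverage, and the correct interval is wider there. At visit 4 the half-width falls from 0.158 to 0.121. At k = 1 and R² = 0 all three models gave a half-width of 0.124 at both visits, so the fuller model costs nothing visible when it is not needed.

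**Step 4: variance by arm.** With the active-arm SD 1.5 times that of placebo, 1:1 allocation and equal spread at the visits, the model SE of the treatment difference was 0.0807 against a true 0.0806. Separate variances by arm matter little for this contrast.

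**The case against.** The strongest defence is that nothing shows the spread differs. At k = 1.0 the intervals are exact, and at 1.1 coverage is within about one percentage point of nominal. SAP 6.7.2 also names no residual structure and gives no code, so a programmer could still fit a suitable one. This stands in part: compound symmetry is the natural reading of the text, but the mis-sizing is conditional and unclear wording is part of the problem.

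Three stronger readings are tempting and not supported.

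- A reader might infer that visit 6 must be the more variable visit, because it follows seasons whose mean birch counts in SAP Appendix D run from 41 to 1053.9 grains/m³, and because some cohort 1 subjects attend it later. These facts show that exposure and timing vary, not that antibody change does. Baseline immunology blood is drawn at visit 1, up to 26 weeks before randomisation, so change at visit 4 may carry seasonal variation too.
- A reader might infer that copying the efficacy model would cure the problem. That model has one seasonal value per subject and lets residual variance differ by arm, not by visit; Step 3 shows that its age-group and cohort terms alone leave visit 6 coverage near 90%.
- A reader might infer that the planned intervals are simply less precise than they should be. That fits the omitted covariates only. Where coverage falls short, the planned interval looks too precise.

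It is also fair that the baseline value is already in the model, which may leave little for other covariates to explain; that cohort and pollen station were not randomisation strata; and that cohort cannot matter in SUB. All of this stands and keeps the covariate part small.

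**Conclusion.** The point holds as a conditional weakness in a supportive analysis. As written, SAP 6.7.2 ties visits 4 and 6 to one variance while reporting inference at each. For SD ratios of 1.0 to 1.5, coverage would run from 95% down to 90.4% at the more variable visit and from 95% up to 98.7% at the other. The ratio is assumed and which visit is more variable is unknown. The coverage figures also assume complete data at both visits.

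Leaving out age group, and cohort and pollen station in the FAS models, does not bias the treatment comparison. It may cost about 0 to 5% in interval width for an assumed R² of 0 to 10%. The primary conclusion and the testing hierarchy do not change.

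**What to change.** In SAP 6.7.2:

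- Replace the random subject effect by an unstructured covariance over visits 4 and 6.
- Add age group as a fixed effect in all three models.
- In the FAS models for IgE and IgG4, also add cohort as a fixed effect and pollen station within cohort as a random effect.
- In the IgE-BF model, add age group only. SUB is confined to cohort 1 and its size is not stated, so a station effect there is not clearly affordable.

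The cost is a few lines of text and code and a few parameters. The covariance goes from two parameters to three, and age group adds one, so IgE-BF gains two. Cohort and the station variance add one each, so the FAS models gain four. The interval at the more variable visit will be wider, correctly so. If the sponsor prefers to keep the model, the SAP should state the covariance structure and say why these factors are left out.
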